## **10.8 Safety**

Safety analyses will be conducted on the safety analysis set. All AEs, including all SAEs and device/procedure related events (including possibly and probably related), will be summarized and tabulated. In addition, the following will be monitored:

- Secondary surgery rate
- Conversion to major knee procedure, such total/partial knee arthroplasty (TKA) and osteotomies
- Overall Failure Rate

## **10.9 Covariate Analyses**

Covariate analyses will be done in FAS for the primary and secondary confirmatory endpoints by including each covariate of interest in the MMRM model, for both study groups, with one MMRM model per covariate listed below. Each covariate will appear in one MMRM. The covariates are the same summarized in the pivotal trial:

- Age (21-<45 vs 45-<65 vs ≥65) and (≥50 vs <50)
- Gender
- BMI (≥30 vs <30)
- Lesion type (Osteochondral vs Chondral) based on ICRS Grade (worst across lesions) = Grade 4b and ICRS Grade (worst across lesions) = Grade 3 or 4a, respectively

A Post Approval Multicenter Open-label

Randomized Controlled Trial of Agili-C™ vs.

Surgical Standard of Care (SSOC) for the  
Treatment of Joint Surface Lesions of the Knee

CLN0021-US

Rev. 8

March 29, 2022

- Single vs multiple lesions
- Kellgren/Lawrence grade (0-1 vs 2-3)
- Lesion size (total area >3 mm^2 vs <=3 mm^2)
- Previous ligament reconstruction (with or without)
- Meniscus status (intact, previous partial meniscectomy, concomitant meniscectomy)
- Pre-Injury Activity Status (active or inactive)
- Smoking History (Current, Past, Never)
- Lesion Location (Femoral Condyle, Trochlea, Mixed)
- US vs OUS Status

Note that the effect of interest is the Treatment x Covariate interaction term in the MMRM model. The tests will be conducted using a 0.15 significance level. Additionally, descriptive statistics will be provided by covariate level.

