9.7 Covariate Analyses

Covariate analyses will be done on the PP population for the primary and secondary confirmatory endpoints by including each covariate of interest in an MMRM model, for both treatment groups, with one MMRM model per covariate listed below. Each covariate will appear in one MMRM.

The covariates are

- Age
- Gender
- BMI
- Lesion type (chondral or osteochondral)
- Number of lesions (single or multiple)
- Level of osteoarthritis (K/L score 0-1 or 2-3)
- Lesion size (total lesion size $\leq 3\text{cm}^2$ or $>3\text{cm}^2$)
- Previous ligament reconstruction (with or without)
- Meniscus status (intact, previous partial meniscectomy, concomitant meniscectomy)
- Activity status (active or inactive)

Note that the effect of interest is the Treatment x Covariate interaction term in the MMRM model, which will be tested using a 0.15 significance level.

Additionally, descriptive statistics will be provided by covariate level for categorical covariates.

For categorical covariates, we will perform an additional analysis, similar to the primary analysis, within each category of the covariate. From this analysis, the credible interval for the treatment effect will be reported for each category and assessed overlap.

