9.8 Demographic and Baseline Characteristics

Demographics and baseline characteristics will be summarized descriptively for the PP, FAS and Safety sets, by treatment group and overall.

- Demographics: age (continuous and categorized), gender (categorical), ethnicity (categorical) and race (categorical)
- Baseline Characteristics include the following:
 - Body Weight Index (BMI)
 - Lesion type (chondral or osteochondral)
 - Number of lesions (single or multiple)
 - Level of osteoarthritis (K/L score 0-1 or 2-3)
 - Lesion size (total lesion size $\leq 3\text{cm}^2$ or $> 3\text{cm}^2$)
 - Previous ligament reconstruction (with or without)
 - Meniscus status (intact, previous partial meniscectomy, concomitant meniscectomy)
 - Activity status (active or inactive)

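### Protocol 10.9 tests treatment-by-age under two unranked categorical codings and treatment-by-BMI only at a cut of 30, where one continuous test each would use the data better

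*Protocol*

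**What the plan says.** Protocol 10.9 plans covariate analyses in the full analysis set (FAS) for the primary and confirmatory secondary endpoints, "with one MMRM model per covariate listed below. Each covariate will appear in one MMRM". Age is entered as "Age (21-<45 vs 45-<65 vs ≥65) and (≥50 vs <50"), which is a three-level coding and a two-level coding. BMI has one two-level coding, cut at 30. The section states: "Note that the effect of interest is the Treatment x Covariate interaction term in the MMRM model". It adds: "The tests will be conducted using a 0.15 significance level". It ranks neither age coding and does not say what follows if they disagree. Its reason for the covariate list is that the pivotal trial summarised the same ones. Protocol 10.11 repeats the 0.15 interaction test and leaves the age coding open.

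The supplied SAP is the 24-month pivotal plan. Its section 9.7 lists age and BMI with no cut points and then says: "Additionally, descriptive statistics will be provided by covariate level for categorical covariates". That wording implies that some listed covariates need not be categorical. SAP 9.8 tabulates age in both forms: "Demographics: age (continuous and categorized"). BMI comes from height and weight at screening. Both variables are therefore available as continuous measurements.

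**The concern.** These interaction tests are the planned evidence on whether the benefit of the device depends on age or BMI. Age deserves a clear answer because Protocol 7.3.2 makes control treatment depend partly on age, so the comparator itself may change with it.

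Two features weaken that evidence. First, grouping discards the variation within groups, which costs power when the effect changes smoothly. Second, age is tested twice with no rule to choose between the results. This raises the chance of a spurious age finding, and it leaves the report unable to give one age conclusion when the tests differ.

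**Working it through.** **1. The plan's own power figure.** Protocol 10.7.1 assumes 120 and 59 subjects, SD 25 and a pooled t-test at one-sided 0.025.

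SE = 25 × sqrt(1/120 + 1/59) = 3.975. With 177 df the noncentral t gives:

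| Difference | Difference / SE | Power | Plan states |
|---|---|---|---|
| 22.5 | 5.66 | 99.99% | 99% |
| 13.9 | 3.50 | 93.5% | 93.5% |
| 11.2 | 2.82 | 80.0% | at least 80% |

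The stated figures reproduce. No power is stated for the interaction tests.

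**2. Power lost by categorising, if effect modification is linear.** The reference is a continuous interaction test at two-sided 0.15, with the effect set so that its power is 80%. With the FAS size of 160 + 79 = 239, the noncentrality is λ = 5.23 (large-sample check: (1.44 + 0.84)² = 5.20). A categorised covariate has noncentrality λ × R², where R² is the share of the covariate's variance that the categories keep. It is tested on 1 df for two levels and 2 df for three.

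R² needs distributions that the documents do not give. **Assumed** ranges:
- Age: normal truncated to the eligible 21-75 years, mean 38-50, SD 9-13.
- BMI: normal truncated at the eligibility limit of 35, mean 25-29, SD 3.5-4.5.

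| Coding | R² kept | Noncentrality | Power (continuous = 80%) |
|---|---|---|---|
| Age, cut at 50 | 0.36-0.67 | 1.9-3.5 | 47-67% |
| Age, three levels | 0.56-0.78 | 2.9-4.1 | 52-63% |
| BMI, cut at 30 | 0.30-0.60 | 1.5-3.2 | 42-63% |

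Worked example, BMI with mean 25 and SD 3.5: R² = 0.296, so sqrt(5.23 × 0.296) = 1.24. Power is approximately Φ(1.24 − 1.44) + Φ(−1.24 − 1.44) = 0.42 + 0.004, or about 0.425.

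Under the same age assumptions, the group aged 65 or over would hold only about 0-8 of the 79 control subjects.

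**3. Two age tests at 0.15.** If the tests were independent, the chance of at least one false signal would be 1 − 0.85² = 27.75%. They are correlated, so this was simulated: 160 and 79 subjects, SD 25, truncated-normal age, 6,000 runs per setting, with a single-outcome linear model standing in for the repeated-measures model.

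| Setting | Cut at 50 | Three levels | Continuous | Either age coding | Codings disagree |
|---|---|---|---|---|---|
| No interaction (three age distributions) | 15% | 15% | 15% | 25% | 19-20% |
| 0.5 points per year | 36% | 36% | 51% | 50% | 27% |
| 0.66 points per year | 50% | 49% | 68% | 64% | 28% |

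The null rows use age mean 42 or 46 and SD 11 or 13. The slope rows use mean 42 and SD 11. Entries in the first four result columns are the share of trials significant at 0.15. With either slope, the single continuous test detects the interaction slightly more often than the two categorical tests together, while keeping its false-positive rate at 15%.

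**The case against.** The strongest reply is that coding in a heterogeneity screen is a matter of choice. Protocol 10.9 carries over the pivotal trial's covariates, and changing the coding could break comparability. This has limited force. The pivotal SAP shows no cut points for age or BMI, and keeping the categories for tables and estimates preserves comparability where it is needed. The pivotal analysis report is not among the documents, so whether these cuts were used there cannot be checked.

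The power loss depends on linearity. A true threshold at one of the cuts would favour that cut, and a three-level coding can find a mid-age effect that a linear term misses. The figure with the control-treatment algorithm is not shown, so an age threshold there cannot be ruled out. This point stands as a cost of the fix, but it does not justify two codings without a ranking.

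The sizes are not properties of this trial. The planned model uses the FAS and repeated visits, and Protocol 10.11 interprets the interaction as an average over follow-up, whereas the check uses one outcome. A reader might also combine the 120 and 59 subjects with a chosen slope and quote an absolute power. For example, 7.5 points per covariate SD gives 67% continuous, 53% for a median split and 50% for a 30/70 split. The documents give no such slope, and 120 and 59 are the assumed month-60 numbers for the primary comparison, so no absolute power can be claimed.

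A reader might infer that two age codings break the sentence "Each covariate will appear in one MMRM". The documents do not establish that. The sentence can mean that covariates are modelled one at a time, and the conflict disappears if each age cut counts as its own covariate. It is ambiguous at most.

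A reader might also infer that the SAP requires continuous coding. It does not state the form in which age and BMI enter the model. It is only compatible with continuous coding.

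Finally, with 13 covariates at 0.15, the chance of at least one false positive is already 1 − 0.85¹³ = 88% if the tests are independent, and a fourteenth test makes it 90%. The duplicate age test therefore matters little for the screen as a whole. It matters for the conclusion about age.

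**Conclusion.** The point holds as a modest improvement. Age is tested under two unranked codings and BMI under one cut, each at 0.15, although continuous values exist and the pivotal SAP sets no cut points. If effect modification is roughly linear, categorising costs power: from 80% to about 42-67% across the assumed distributions. The direction is general under linearity, but the size is conditional on those assumptions. The doubled age test raises the false age signal from 15% to about 25%. Its two results differ in about 20% of trials without an interaction and 27-28% with the moderate linear ones simulated.

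None of this bears on the primary superiority decision. Trial success rests on the primary endpoint, and no labelling claim is tied to these tests.

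**What to change.** In Protocol 10.9, state that the deciding treatment-by-age and treatment-by-BMI interaction tests use continuous age and continuous BMI, one test of each per endpoint. Keep the listed age and BMI categories for descriptive tables and subgroup estimates, so that these remain comparable with the pivotal trial. Align the wording with SAP 9.7 and Protocol 10.11. If continuous coding is not adopted, the minimum is one sentence naming the age coding that decides.

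No new data are needed. The re-coding covers six continuous endpoints (overall KOOS and five subscales) × two covariates = 12 repeated-measures models, plus the responder endpoint. The statistical cost is that a linear term could miss a threshold or non-monotone pattern, which the retained category estimates would still show.

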## **10.10 Sensitivity Analyses**

As noted, the Bayesian and MMRM analyses implicitly impute missing data over time.

These implicit imputations are valid under the missing at random (MAR) assumptions. The following sensitivity analyses will be performed to evaluate the if primary results depend on this assumption.

- Worst-Case Scenario assumes all missing values among Agili-C are equal to most negative observed change score, if feasible, else equal to 0 - [baseline value] and all missing values among SSOC are equal to most positive observed change score, if feasible, else equal to 100 - [baseline value].
- If the superiority finding is lost in the Worst-Case Scenario, a tipping point analysis will be performed. In this analysis, for each value X from the worst observed control subject to the best observed control subject, and for each value Y from the worse observed Agili-C subject to the best Agili-C subject, the primary analysis will be calculated imputing all missing Control subjects as X and all Agili-C subjects as Y, producing a grid over all plausible values for the control and Agili-C subjects. This grid

includes a worst case scenario, where all control subjects are imputed with the best observed control value and all Agili-C patients imputed as the worst observed Agili-C patient. The grid also includes a best case scenario, imputing controls as the worst control patient and Agili-C patients as the best observed Agili-C patients. The tipping point curve can be observed looking in the grid for the required values of (X,Y) that result in primary analysis success.

### **10.11 Poolability analyses**

MMRM will be used to evaluate poolability and heterogeneity of treatment effects across subgroups. The following fixed factors will be included:

- Covariate by group
- Covariate by visit
- Covariate by visit by group

The effect of interest is the Treatment x Covariate interaction term in the MMRM model, which will be tested using a 0.15 significance level. The interpretation of this interaction is a treatment group difference in the mean improvement over time averaging across follow-up visits. The significance of the three-way interaction is also summarized. The three-way interaction reflects covariate differences in the way group differences vary over time.

### **11.0 Interim Analysis**

Information regarding interim study progress and results, including: number of study sites, number of patients, and effectiveness (primary & confirmatory secondary endpoints on FAS population) and safety endpoints results, will be posted on the FDA PAS webpage after each interim progress report:

Milestone	Expected Date of Completion
1. Follow-up is completed for all study participants	February 2025
2. Interim Reports	October 2022

A Post Approval Multicenter Open-label  
Randomized Controlled Trial of Agili-C™ vs.  
Surgical Standard of Care (SSOC) for the  
Treatment of Joint Surface Lesions of the Knee

CLN0021-US  
Rev. 8  
March 29, 2022

	October 2023
	October 2024
3. Final study report	Q2 2025

## **12.0 Compliance with IRB/EC Regulations**

This study will be conducted in accordance with applicable regulations (U.S. 21 CFR for all centers and country specific regulations). The PI must obtain approval from a properly constituted IRB/EC prior to initiating the study and re-approval or review as required. The Sponsor is to be notified immediately if the responsible IRB/EC has been disqualified or if proceedings leading to disqualification have begun. Copies of all IRB/EC correspondence with the PI should be provided to the Sponsor.

## **13.0 Compliance with Electronic Records; Electronic Signatures Regulations**

This study will be conducted in compliance with the regulations on electronic records and electronic signature.

## **14.0 Changes to the Protocol**

If it becomes necessary to amend the Clinical Investigation, the nature of the amendment will be agreed between the Sponsor and the Principal Investigator(s) and this will be recorded with a justification for the amendment. The appropriate IRB/EC and other applicable oversight committee as required will be informed of any amendments prior to implementation.

## **15.0 Subject Confidentiality**

A report of the results of this study may be published or sent to the appropriate health authorities, but the subject's names will not be disclosed in these documents. Appropriate

	A Post Approval Multicenter Open-label Randomized Controlled Trial of Agili-C™ vs. Surgical Standard of Care (SSOC) for the Treatment of Joint Surface Lesions of the Knee	
		CLN0021-US Rev. 8 March 29, 2022

precautions will be taken to maintain confidentiality of medical records and personal information.

## **16.0 Subject Privacy**

Written authorization will be obtained from each subject prior to enrollment into the study in accordance with the applicable privacy requirements (e.g., the Health Insurance Portability and Accountability Act Standards for HIPAA) and any local national regulations.

## **17.0 Documentation**

The PI will maintain a confidential Subject Contact List with the names and contact information for all subjects recruited for participation in the study, whether s/he enrolled, and reason(s) for those who do not enroll. Each subject will receive a unique Subject Number. The Subject Contact List will link the subject by name and Subject Number to this study. The PI will track the participation of enrolled subjects on a Study Visit Log, which identifies subjects by number and initials only.

## **18.0 Source Documents**

Individual Subject records will be maintained in the PI's Source Documents (SDs). Source documentation is generally considered to be the document on which the information or data point was first recorded. SDs may include a subject's medical records, hospital charts, clinic charts, and the PI's study files as well as the results of diagnostic tests. Pertinent records related to the study, e.g., the subject's medical chart, will be made available to the Sponsor representative on request with due precaution to protect the privacy of the subject. Personal identifying information (except subject initials) will be removed from any photocopies of relevant medical records and replaced with the unique Subject Number before submission to the Sponsor. The PI will protect the confidentiality of all subjects' records within applicable laws.

	CLN0021-US-Investigational Plan A Post Approval Multicenter Open-label Randomized Controlled Trial of Agili-C™ vs. Surgical Standard of Care (SSOC) for the Treatment of Joint Surface Lesions of the Knee	Document Number: CLN-0000002 Document Version: 8.0 Effective Date: 08-Jun-2022 (GMT+2) Page 60 of 80
		CLN0021-US Rev. 8 March 29, 2022

## **18.1 Case Report Form (CRF) Completion**

The PI is responsible for ensuring that data are properly recorded on each subject's CRFs and related documents. Source data must exist for all data entered in the CRF.

## **18.2 Retention of Documentation**

Essential documents are any records that demonstrate the compliance of the subject, PI, Sponsor, and Monitor with the study protocol, with standards of GCP, and with all applicable regulatory requirements. Essential documents (including but not limited to study-related correspondence, subject records, subject privacy documentation, records of the distribution and use of all investigational devices, and copies of CRFs) should be retained and available for audit by the Sponsor's auditor and regulatory authorities According to applicable FDA and specific country regulation. These documents should be retained for a longer period, however, if mandated by the applicable regulatory requirements, by conditions imposed by the IRB/EC, or by an agreement with the Sponsor. It is the responsibility of the Sponsor to inform the PI when these documents no longer need to be retained. The Sponsor requires that it be notified in writing if the PI chooses to store the records at a different physical address than the site address or if the PI wishes to relinquish ownership of the data so that mutually agreed-upon arrangements can be made for transfer of ownership to a suitably qualified, responsible person.

## **19.0 Monitoring Procedure**

Appropriately trained representatives of the Sponsor will monitor the conduct of the trial at each investigational site, including visits to the site to review, audit, and retrieve copies of study-related documents. It is the responsibility of the PI to be present or available for consultation and to ensure that the Monitor has access to all study-related records during scheduled monitoring visits. The Monitor will review device accountability records and completed CRFs to ensure completeness and consistency with the source records and compliance with the protocol requirements. Study monitoring will be performed by a certified

	CLN0021-US-Investigational Plan A Post Approval Multicenter Open-label Randomized Controlled Trial of Agili-C™ vs. Surgical Standard of Care (SSOC) for the Treatment of Joint Surface Lesions of the Knee	Document Number: CLN-0000002 Document Version: 8.0 Effective Date: 08-Jun-2022 (GMT+2) Page 61 of 80
		CLN0021-US Rev. 8 March 29, 2022

CRO, in compliance with recognized GCP, FDA's IDE guidance documents. On-site monitoring visits will ensure SDV and will include at least an initiation visit and any other visits that might be required during the study, and a final visit at the close of the study.

## **20.0 Regulatory and Health Authority Audits**

The FDA, European Union authorities or local state health authorities (where applicable) may request access to all study records, including source documents for inspection. The PI and hospital staff are required to cooperate with these audits. The PI must notify the Sponsor of any health authority audit as soon as notification of such audit is made. A representative or designee of the Sponsor may also conduct similar audits and may be present during health authority audit.

## **21.0 Handling of Biological Specimens**

Tissue biopsy(ies) might be obtained if clinically indicated. Biopsies can include: implants or parts of implants, synovial tissue, synovial fluid, cartilage, bone etc. Biopsies will be sent to an independent laboratory approved by the Sponsor, for analysis, as per the laboratory instructions. The specimens will be sent via an over-night delivery service. Routine biopsies are not recommended in this study. Biopsy samples for histological evaluation will be placed in formalin, securely sealed, and shipped to an independent laboratory for processing using established techniques and stains, such as hematoxylin and eosin (H&E), tri-chrome, or Safranin-O stain. A single board-certified pathologist who is experienced in histological evaluation of joint repair procedures will evaluate all slides from the study and will comment on the types and relative quantities of cells observed, the presence and status of the implant, the overall level of inflammation and any other interesting features. At the conclusion of the study, the laboratory and the pathologist will submit all tissue samples and slides to the Sponsor for retention with other essential study records (Section 18.2). The tissue samples and slides will not be used for any other purpose. Subject privacy concerns and biohazard

**A Post Approval Multicenter Open-label Randomized Controlled Trial of Agili-C™ vs. Surgical Standard of Care (SSOC) for the Treatment of Joint Surface Lesions of the Knee**

CLN0021-US  
Rev. 8  
March 29, 2022

handling precautions will be paramount. All evaluation shall be conducted according to GCP/GLP.

